6.2. Analysis of Study Population

6.2.1. Patient Disposition

Patient disposition will be summarized in terms of counts and percentages for all patients who have signed the informed consent regardless of seribantumab treatment. The following patient disposition categories will be summarized:

- Patients screened
- Patients who enrolled in the study
- Patients treated with seribantumab
- Patients discontinued from seribantumab
- Patients who terminated the study

For patients who discontinued study treatment, or terminated the study, a summary will be provided by reason.

The number and percentage of patients in each defined analysis population may also be tabulated.

All patient disposition data will be listed.

6.2.2. Protocol Deviations

Protocol deviations will be identified and reported by the process described in the current version of the study Protocol Deviation Plan. Protocol deviations considered reportable in the clinical study report per the study Protocol Deviation Plan will be summarized and listed by-patient.

6.2.3. Demographics and Baseline Characteristics

Demographic characteristics will be collected during the Screening period. Gender, race, and ethnicity will be summarized using frequencies and percentages. If female, the frequencies and percentages of childbearing potential will be summarized. Age at Screening will be summarized using descriptive statistics. Demographic and baseline characteristics will be summarized based on the safety population. Additional summaries based on other analysis populations may also pe performed.

Baseline height (cm), body weight (kg) will be summarized with descriptive statistics and Eastern Cooperative Oncology Group (ECOG) performance status will be summarized using frequencies and percentages.

Demographics and baseline characteristics will be listed by-patient.

6.2.4. Medical History

A medical history will be collected during Screening. All pertinent prior medical conditions, surgeries or other medical procedures, allergies, and concomitant medications will be collected.

The reported medical history terms will be coded using the MedDRA v26.0 or later. Summary analyses for medical history will be based on Safety Population and will be summarized by system organ class (SOC) and preferred term (PT). Patients may have more than one reported medical history event for each SOC and PT but will be only counted once within each SOC and PT classification.

Reported medical history data will be presented in a by-patient listing.

6.2.5. Primary Cancer History

Primary cancer history will be collected during Screening. Continuous variables including time from initial histologic/cytologic diagnosis (months) and time from last progression will be summarized with descriptive statistics. Categorical variables including primary cancer type, tumor stage at time of diagnosis, histology/cytology, grade, tumor stage at trial entry, NRG1 Fusion detected, NRG1 testing method, and other genomic findings will be summarized in count and percentage.

Primary cancer history data will be presented in a by-patient listing.

The analyses will be based on Safety Population. The prior systemic anti-cancer treatments, prior cancer radiation therapy, and prior cancer surgery will be collected during Screening.

For systemic anti-cancer treatments, the number and percentage of patients, the line of therapy setting, duration of therapy, best overall response (defined in order of CR, PR, SD, PD, NON-CR/NON-PD, NE), and reason for discontinuing will be summarized. The reported cancer therapy terms will be coded using the World Health Organization (WHO) Drug Dictionary (Version Global B3, March 2020 or later). Prior cancer therapies will be summarized by Anatomical Therapeutic Chemical (ATC) and PT. A patient will be counted only once within an ATC classification but may contribute to two or more PTs in the same classification.

For prior radiation therapy and prior cancer surgery, the number and percentage of patients, the radiation location, duration of radiation therapy, total dose in Gy, surgery intention will be summarized. The type of surgery will be coded using MedDRA v26.0 or later. The surgeries will be summarized by SOC and PT. A patient will be counted only once within a SOC classification but may contribute to two or more PTs in the same classification.

All prior therapies will be listed, including prior systemic anti-cancer treatments, prior radiation therapy and prior cancer surgery.

6.2.7. Prior & Concomitant Medications

The medications collected will be coded using WHO Drug Dictionary (Version Global B3, March 2020 or later). The prior and concomitant medications will be summarized by ATC and PT. A patient will be counted only once within an ATC classification but may contribute to two or more PTs in the same classification. Frequency ordering will be used for the table presentation (i.e. order by the overall grouping in descending frequency for each ATC and for each PT within each ATC).

All prior and concomitant medications will be presented in listings.

6.2.8. Concomitant Medical Procedures

The number and percentage of patients will be summarized. All medical procedures will be coded by using MedDRA v26.0 or later. The medical procedures will be summarized by SOC and PT. A patient will be counted only once within a SOC classification but may contribute to two or more PTs in the same classification. Frequency ordering will be used for the table presentation (i.e. order by the overall grouping in descending frequency for each SOC and for each PT within each SOC).

All concomitant medical procedures will be presented in a data listing.

6.2.9. Subsequent Cancer Therapies

Subsequent cancer therapies (subsequent cancer therapy, cancer surgery and radiation therapy) will be collected during every survival follow-up.

For subsequent cancer therapy, regimen start/stop dates, and ongoing status will be recorded. The number and percentage of patients treated with a subsequent cancer regimen will be summarized. The reported cancer therapy terms will be coded using WHO Drug Dictionary (Version Global B3, March 2020 or later). Subsequent cancer therapies will be summarized by ATC and PT. A patient will be counted only once within an ATC classification but may contribute to two or more PTs in the same classification.

For subsequent cancer surgery, the number and percentage of patients who have surgery therapies, palliative/curative intent will be summarized. For subsequent radiation therapy, the number and percentage of patients who have radiation therapies, palliative/ curative intent, therapy location, total dose in Gy will be summarized.

The surgery procedures will be summarized by SOC and PT. A patient will be counted only once within a SOC classification but may contribute to two or more PTs in the same classification.

All the subsequent therapies will be listed.

6.3. Efficacy Analyses

All efficacy analyses will be performed by cohort. Analyses for the cohort 1 primary efficacy analysis population will be intended to support a potential registration With the exception on the handling of tumor assessments after the initiation of new anticancer therapy as described in Sections 5.1 and 5.2, all data from scheduled or unscheduled assessments will be included in the efficacy analyses.

All efficacy analysis will be analyzed by investigator assessments only, independent radiographic review was not done due to Sponsor decision to end the study prior to full enrollment.

6.3.1. Objective Response Rate

The point estimate of the ORR along with the 2-sided 95% exact Clopper-Pearson CI will be presented.

The best overall response (CR, PR, SD, PD, NE) will also be tabulated to show the number and percentage of patients in each response category.

6.3.2. **Progression-free Survival**

PFS will be estimated using the Kaplan-Meier method and will be presented graphically. Sensitivity analysis based on the alternative censoring rules described in Table 1 will be provided.

The number and percentage of patients experiencing a PFS event and patients censored will be summarized. The median, 25th percentile, 75th percentile, minimum and maximum will be provided along with the 95% CI for the median. The proportion and 95% CI for the number of patients progression-free at clinically significant time points (e.g., 6 months, 12 months) from the date of the first dose will be provided. Other clinically relevant timepoints may also be included if data warrant.

6.3.3. Overall Survival

OS will be estimated using the Kaplan-Meier method along with the Kaplan-Meier plot. The number and percentage of deaths and patients censored will be summarized. The median, 25th percentile, 75th percentile, minimum and maximum will be provided along with the 95% CIs for the median. The proportion and 95% CI for the number of patients alive at clinically significant time points (e.g., 6 months, 12 months) from first treatment will be provided. Other clinically relevant timepoints may also be included if data warrant.

6.3.4. Duration of Response

DoR will be estimated using the Kaplan-Meier method along with the Kaplan-Meier plot. The number and percentage of patients experiencing a DoR event and patients censored will be summarized. The median, 25th percentile, 75th percentile, minimum and maximum will be provided along with the 95% CI for the median. The proportion and 95% CI for the number of patients with durable responses at 6 months and 12 months from the onset of response will be provided. Other clinically relevant timepoints may also be included if data warrant.

6.3.5. Clinical Benefit Rate

The CBR along with exact Clopper-Pearson 95% CI will be presented.

6.3.6. Interim Futility Analysis

A pre-planned interim futility analysis based on investigator assessed ORR will be conducted after 20 patients are enrolled in the cohort 1 primary efficacy analysis population and have been followed for at least one tumor assessment (i.e., 6 weeks +/- 2 weeks). Should four or more objective responses be observed at the time of the interim analysis, enrollment to cohort 1 for the primary analysis population will continue until a minimum of 55 patients. The futility analysis will be considered non-binding as factors other than ORR may be factored in (such as depth of response, duration of response, tumor type and fusion partner).

6.4. Safety Analyses

The assessment of the incidence of adverse events during the study will consist of the recording of any AEs, SAEs, DLTs, etc. Safety will also be assessed through clinical laboratory evaluations, immunogenicity assessments, vital signs, electrocardiograms (ECGs), physical examinations, ECOG performance status, and prior and concomitant medication reporting.

The safety analysis will be based on the Safety Population and will be presented by cohort (cohort 1 primary efficacy analysis population, cohort 1, cohort 2, cohort 3) and all cohorts combined.

6.4.1. Extent of Exposure

Descriptive statistics will be provided for total treatment duration, total dose planned, actual total dose administered, and relative dose intensity.

The number and percentage of patients initiating a given number of treatment cycles and seribantumab infusions will be summarized. A cycle will be defined as 28 days. In addition, the number and percentage of patients with dose modification, dose interruption, or missed dose will be summarized, along with the reason.

The seribantumab administration data will be presented in a by-patient listing.

6.4.2. Adverse Events

Patient incidence will be summarized in tables. Frequency ordering will be used for the table presentation (i.e. order by the overall grouping in descending frequency for each SOC and for each PT within each SOC).

An overview of adverse events will be provided which summarizes the patient incidence of the following. This overview will include the number and percentage of patients with:

- Any AEs;
- Any TEAEs;
- Any drug related TEAEs;
- Any serious adverse events (SAEs);
- Any serious TEAE (TESAEs);
- DLTs;
- CTCAE grade 3/4/5 TEAEs;
- CTCAE grade 3/4/5 TEAEs related to seribantumab;
- TEAEs leading to dose reduction or interruption of study drug;
- TEAEs leading to discontinuation of study drug;
- TEAEs resulting in Death.

The number and percentage of patients with AEs will be tabulated by the highest CTCAE Grade, SOC, and PT. DLTs, TEAEs, TEAEs related to study drug will be summarized in the same manner.

TEAEs will also be summarized by SOC and PT. DLTs, CTCAE Grade 3/4/5 TEAEs, TESAEs, drug-related TEAEs, drug-related CTCAE Grade 3/4/5 TEAEs, AEs leading to dose reduction or interruption of study drug, and AEs leading to discontinuation of study drug will be summarized in the same manner.

For all above summaries, patients with multiple adverse events will be counted only once per SOC and PT.

Listings will be presented for TEAEs and TESAEs.

6.4.3. Clinical Laboratory Evaluations

Clinical laboratory evaluations will be summarized using descriptive statistics for select laboratory parameters (e.g. serum or plasma chemistry, complete blood count) including

absolute measurements and changes from baseline by scheduled time of evaluation. Changes from baseline by scheduled time of evaluation will include EOT visit, maximum post-treatment value, and minimum post-treatment value. Both scheduled and unscheduled post-treatment visits will be considered for the summaries of the maximum and minimum post-treatment values.

Abnormal laboratory results will be graded according to NCI CTCAE v5.0 as applicable.

Clinical laboratory evaluations will be listed by patient and abnormal values will be flagged.

6.4.4. Vital Signs

Descriptive statistics will be provided for vital signs measurements (systolic and diastolic blood pressure, pulse rate, respiratory rate, body temperature, and weight). Actual observed values and changes from baseline by scheduled evaluation, and maximum and minimum post-treatment values will be presented.

Both scheduled and unscheduled post-treatment values until the EOT will be considered for summaries of the minimum and maximum on-treatment values. In addition, box plots of change from baseline values by visit for systolic and diastolic blood pressure and pulse rate will be produced.

All vital signs assessments will be presented in a by-patient listing.

6.4.5. Electrocardiograms

Note that the mean of the triplicate readings will be obtained at Screening for each patient prior to summarizing.

Continuous ECG parameters (Cardiac Rate, PR, RR, QRS, QT, QTcF) will be summarized using descriptive for actual values and for changes from baseline by scheduled time of evaluation, including the maximum post-treatment value. Both scheduled and unscheduled post-treatment values will be considered for summaries of the maximum post-treatment values.

The Fridericia-corrected QT interval (QTcF) will be calculated as $QTcF = QT/(RR)^{1/3}$ for the above summaries.

- Increase from baseline QTcF > 30 ms
- Increase from baseline QTcF > 30 ms and $QTcF \le 60$ ms
- Increase from baseline QTcF > 60 ms

Box plots or other graphical summaries may be produced for QTcF absolute and change from baseline values if warranted after data review.

Overall evaluation of ECG is also collected at each visit in terms of normal or abnormal, and the relevance of the abnormality is termed as "clinically significant" or "not clinically significant", this information may be summarized.

6.4.6. Physical Examinations

The overall physical examination result at each time point (including scheduled and unscheduled will be listed by-patient.

6.4.7. ECOG Performance Status

For patients with ECOG performance status assessments, the performance status at each visit on study and worst post-baseline assessment will be presented using frequencies and percentages. Both scheduled and unscheduled visits will be considered in determination of the worst post-baseline assessment.

ECOG performance status results will be presented in a by-patient listing.

6.4.8. Other Safety Assessments

Results from other safety assessments (e.g. pregnancy test) will be presented in by-patient listings if applicable.

6.5. Covariates and Subgroups

The following covariates and subgroups are of interest:

- Tumor type (NSCLC vs other tumors)
- Fusion partner (ADAM9, AGRN, APP, ATP1B1, BAG4, CD74, CDH1, COX10-AS1, DIP2B, DPYSL2, FUT10, GDF15, HMBOX1, IL1RL2, ITGB1, MDK, MRPL13, NOTCH2, PARP8, POMK, RBPMS, RNF169, ROCK1, SDC4, SETD4, SLC3A2, TMPRSS3, TNC, TSHZ2, VAMP2, VTCN1, WHSC1L1, ZMYM2)

Additional efficacy and safety analysis may be performed by subgroups for cohort 1 primary efficacy analysis population. Waterfall plot of responses will be provided by fusion partner.

6.6. COVID-19

Due to the COVID-19 pandemic, additional analyses (e.g., sensitivity analysis) may be performed to assess the impact of COVID-19 on clinical trial data.

Applicable data collected in relation to COVID-19 on the CRF will be summarized as appropriate and/or included in data listings.

Protocol deviations resulting from COVID-19 will be recorded and included in the protocol deviation listing.

6.7. Pharmacokinetic Analysis

Plasma concentrations by patient, cycle, day, and time will be obtained and documented at various time points during the treatment with seribantumab.

If applicable, additional PK analysis and methods will be described in a standalone PK analysis plan.

PK concentration results will be presented in a by-patient listing.

7. GENERAL INFORMATION

7.1. Statistical Software

The creation of analysis datasets and statistical analyses will be done using SAS[®] version 9.4 or higher. The Medpace standard operating procedures (Medpace Standard Operating Procedures GL-DS-02-S4 and GL-DS-03-S3, or newest version at the time of analysis if applicable) will be followed for the validation of all SAS programs and outputs.

7.2. Format of Tables, Listings, and Figures

The format of tables, listings, and figures will be described in a stand-alone programming specifications document. The programming specification document will be prepared before database lock (or interim data lock for analyses presented at interim analysis).

8. CHANGES FROM PROTOCOL-SPECIFIED ANALYSIS

An independent central review of scans was not done due to Sponsor decision to end the study prior to full enrollment. Therefore, the primary efficacy endpoint and secondary efficacy endpoints utilizing independent radiologic review will not be analyzed.

The following exploratory endpoints in Protocol 7.0 will not be analyzed:

- To evaluate if mechanistically linked exploratory biomarkers from tumor tissue or blood samples correlate with clinical outcomes
- To evaluate changes from baseline in quality of life, as measured by the European Organization for Research and Treatment of Cancer (EORTC) Quality of Life Questionnaire-Core 30 (QLQ-C30)

For Cohort 1 Primary Efficacy Analysis Population definition, "based on independent central reviews" was removed from the last criteria.

Cohort 2 and Cohort 3 Efficacy Analysis Population, intended for exploratory efficacy analysis, will not be analyzed.

9. **REFERENCES**

Brookmeyer, R., & Crowley, J. (1982). A confidence interval for the median survival time. *Biometrics*, 29-41.

Kalbfleisch, J. D. & Prentice, R. L. (2002). *The statistical analysis of failure time data* (2nd ed.). Hoboken, NJ: John Wiley & Sons, Inc.

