
Statistical Considerations and Data Reporting:
	
General:
 
In general, all analyses will follow the multi-cohort nature of the study design. Categorical variables will be summarized by frequency distributions (number and percentages of patients) and continuous variables will be summarized by descriptive statistics (mean, standard deviation, median, minimum, maximum).
 
Analysis Populations:
 
The analysis populations to be used for the planned statistical analyses include:
 
Efficacy Analysis Populations
 
 • Cohort 1 primary efficacy analysis population 
Analyses of the Cohort 1 primary efficacy analysis population will be intended to support a potential registration. It will include Cohort 1 patients enrolled in this study who meet all criteria listed below:
 
 • Centrally confirmed NRG1 gene fusion. • Received at least one dose of seribantumab at 3,000 mg QW dosing regimen (starting with Protocol Version 3.0 and later). Patients in the safety-run in (enrolled under Protocol Version 2.0 or earlier) will be included if they received seribantumab at 3,000 mg QW beyond induction/re-induction. • Received at least one prior standard therapy in the locally advanced or metastatic setting. • At least one measurable lesion at baseline as assessed per RECIST v1.1 based on independent central review. 
 • Cohort 2 and Cohort 3 efficacy analysis population 
These populations will be used for exploratory efficacy analysis by investigator-assessments for each cohort, respectively. All patients enrolled in each cohort who received at least one dose of seribantumab and had at least one measurable lesion at baseline assessed per RECIST 1.1 based on investigator assessments will be included in the analysis. With the release of Protocol Version 5.0, Cohort 3 was closed to enrollment. Under Protocol Version 5.0/Protocol Administrative Letter 8.0, Cohort 2 was closed to enrollment.
 
Safety analysis population: The safety analysis population includes patients receiving at least one dose of seribantumab therapy across any of the three treatment cohorts (e.g., Cohort 1, 2, and 3) and across any of the

seribantumab dosing regimens. The safety population will be used for the overall safety analysis.

Primary Efficacy Analysis:

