10.2.2. Cohort 2 and Cohort 3 Efficacy Analysis Population

These populations will be used for exploratory efficacy analysis for each cohort, respectively. All patients enrolled in each cohort who received at least one dose of seribantumab and had at least one measurable lesion at baseline assessed per RECIST 1.1 based on investigator assessments will be included in the analysis. With the release of Protocol Version 5.0, Cohort 3 was closed to enrollment. Under Protocol Version 5.0/Protocol Administrative Letter 8.0, Cohort 2 was closed to enrollment.

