DoR by investigators: DoR based on the investigator assessments will be analyzed similarly as described for the respective endpoint based on the independent radiographic reviews. This is considered a sensitivity analysis.

Progression-free Survival (PFS): PFS is defined as the time from the date of seribantumab treatment initiation (Dose 1) to the first documented radiographical progression of disease using RECIST v1.1, or death from any cause, whichever comes first. The Kaplan-Meier method will be used to estimate PFS. In addition to the Kaplan-Meier plot of PFS, the median PFS time, 6-month, and 12-month PFS rates will be estimated along with 95% CI. PFS analysis will be performed separately based on central radiographic review and investigator assessments. Additional sensitivity analysis of PFS may be performed using different censoring rules. These sensitivity analyses will be detailed in the SAP.

Overall Survival: OS is defined as the time from the date of treatment seribantumab treatment initiation (Dose 1) to the date of death from any cause. The Kaplan-Meier method will be used to estimate OS. In addition to the Kaplan-Meier plot of OS, the median OS time, 6-month, and 12-month survival rates will be estimated, along with 95% CI.

Clinical Benefit Rate (CBR): Clinical benefit rate is defined as the proportion of patients who achieve PR, CR, or SD which is maintained through at least 24 weeks per RECIST v1.1. Tumor assessments after the initiation of new anticancer therapy should not be used to derive the CBR. Patients with no baseline disease assessment or no evaluable post-baseline disease assessments (i.e., NE) or with ongoing SD but short of 24 weeks at the time of analysis will be considered as not having attained clinical benefit and included in the denominator in the calculation of the CBR. CBR will be summarized similarly as the ORR with both point estimate and 95% Clopper-Pearson CI provided. CBR analysis will be performed separately based on central radiographic review and investigator assessments.

Secondary efficacy endpoints will also be assessed by subgroups defined by the predefined factors listed in Section 10.8.

10.5.3. Exploratory Efficacy Analysis for Cohorts 2 and 3

Efficacy analyses of the primary efficacy endpoint and secondary efficacy endpoints for Cohorts 2 and 3 will be performed separately using the same methods described above. For the ORR, DoR, CBR, and PFS endpoints, investigator assessments will be used.

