3. STUDY OVERVIEW

3.1. Study Design

This study is an open-label, international, multi-center, Phase 2 study in adult patients with advanced or metastatic solid tumors, which harbor the NRG1 gene fusion based upon local testing. The design of the study is summarized in Figure 1.

All patients will be determined to be NRG1 gene fusion positive based on local testing of tumor tissue per local laboratory directed analyses prior to initiating further screening procedures. After all screening procedures and determination of eligibility for study treatment have been completed, eligible patients will be assigned by the Sponsor to the appropriate cohort based upon prior treatment history. Patients will be assigned to Treatment Cohorts as follows:

Cohort 1: Patients with NRG1 gene fusions who are ERBB/HER2/HER3 treatment-naïve AND harbor NRG1 gene fusions with an EGF-like domain intact. Cohort 1 will include at least 55 patients with tumors that progressed on or are intolerant to ≥ 1 prior standard first-line therapy in the metastatic setting.

Cohort 2: Enrollment to Cohort 2 was closed under Protocol Version 5.0/Protocol Administrative Letter 8.0. Patients with NRG1 gene fusions with an EGF-like domain intact, who received ≥ 1 prior standard first-line therapy in the locally advanced or metastatic setting including at least one ERBB/HER2/HER3 directed treatment are ineligible for study participation.

Cohort 3: Enrollment to Cohort 3 was closed under Protocol Version 5.0 and later. Patients with NRG1 fusions without an EGF-like domain (including but not limited to NRG1-PMEPA1, NRG1-STMN2, PCM1-NRG1 and INTS9-NRG1) and patients with NRG1 fusions and other molecular aberrations lacking standard treatment options, AND patients unable to provide tissue for central confirmation of NRG1 gene fusion status are ineligible for study participation under Protocol Version 5.0.

*Cohort 1 will include at least 55 patients that have received ≥1 prior standard first-line therapy in the metastatic setting. **More than 10 patients may enroll under Cohorts 2 and 3 with Sponsor approval. Shaded box indicates cohort is closed to enrollment

EGF = epidermal growth factor; ERBB = receptor tyrosine-protein kinase erbB-3; HER = human epidermal growth factor receptor; NRG1 = Neuregulin-1

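### SAP Section 8 drops the exploratory Cohort 2 and Cohort 3 efficacy analyses planned in Protocol 7.0 without giving a reason, and the reasons given nearby do not cover them.

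*SAP*

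**What the plan says.** **Protocol 7.0.** Section 10.5.3 commits to the analyses: "Efficacy analyses of the primary efficacy endpoint and secondary efficacy endpoints for Cohorts 2 and 3 will be performed separately using the same methods" as for Cohort 1. It then names the assessor: "For the ORR, DoR, CBR, and PFS endpoints, investigator assessments will be used". The synopsis agrees: "These populations will be used for exploratory efficacy analysis by investigator-assessments for each cohort, respectively". Section 10.2.2 defines the population as "All patients enrolled in each cohort who received at least one dose of seribantumab" and who had measurable disease at baseline by investigator assessment. The same section records that Cohort 3 closed to enrollment with Protocol Version 5.0, and Cohort 2 under Version 5.0 with Administrative Letter 8.0.

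**SAP 1.0 (11 March 2024).** Section 8 opens with: "An independent central review of scans was not done due to Sponsor decision to end the study prior to full enrollment". The consequence it draws is that endpoints relying on independent review will not be analyzed. Further down, as a separate item, it says: "Cohort 2 and Cohort 3 Efficacy Analysis Population, intended for exploratory efficacy analysis, will not be analyzed". No reason is attached.

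Section 4.1 defines an efficacy population for Cohort 1 only. Section 6.3 nevertheless says "All efficacy analyses will be performed by cohort", and moves all efficacy to investigator assessment. Sections 6.1 and 6.4 keep safety summaries for Cohorts 2 and 3.

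**The concern.** Two of the three cohorts lose every planned efficacy result in one sentence, and the reader is not told why. The study is open-label, so investigator-assessed responses could have been known to the sponsor when the SAP was written. The SAP describes the decision to end the study in the past tense, so the removal was fixed in the SAP after that decision. A removal made at that point with no reason given cannot be defended against the suggestion that it depended on results.

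The information at stake is modest but hard to replace. Cohort 2 holds patients already treated with ERBB/HER2/HER3-directed therapy. Cohort 3 includes patients whose fusions lack an EGF-like domain, which Protocol 1.2 regards as unlikely to be oncogenic. The planned report would give safety for these patients and no efficacy.

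**Working it through.** **The plan's own figure.** The only sizing statement is for Cohort 1: 55 patients, about 90% power for the exact 95% lower bound to exceed 20% if the true ORR is 40% (Protocol 10.3, SAP 3.4). The smallest passing count is 18: 18/55 has a lower bound of 20.7%, and 17/55 has 19.1%. Power = P(X ≥ 18 | n = 55, p = 0.40) = 0.893, so the figure reproduces. It does not depend on Cohorts 2 and 3, and restoring their analyses leaves it unchanged. No sample size or power is stated for those cohorts.

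**Does any reason given nearby reach Cohorts 2 and 3?**

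| Possible reason | What the documents say | Covers Cohorts 2 and 3? |
|---|---|---|
| Central review not done | SAP 8 ties this to endpoints that use independent review. Protocol 10.5.3 assigns the Cohort 2 and 3 tumor endpoints to investigators. SAP 3.6 limits central review to Cohort 1. | No |
| No reading of scans available | SAP 6.3 analyzes efficacy by investigator assessment, the method already specified for these cohorts. OS needs no image reading. | No |
| Study ended before enrollment was complete | Both cohorts were already closed under Protocol Version 5.0. | No |
| No patients in these cohorts | Safety is still to be tabulated for each (SAP 6.1, 6.4), which implies treated patients. Counts are not given. | Not indicated |

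**How precise could the results be?** Actual cohort sizes are not in the documents. The footnote to the study schema reads "More than 10 patients may enroll under Cohorts 2 and 3 with Sponsor approval". It does not say whether 10 is per cohort or combined, and it is not a count of patients enrolled. Sizes below are therefore assumptions. Intervals are exact Clopper-Pearson 95%; for zero responses the upper bound is 1 − 0.025^(1/n), so for n = 10 it is 1 − 0.025^(0.1) = 30.8%.

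| Assumed n | 0 responses: upper bound | 20% observed: interval |
|---|---|---|
| 5 | 52.2% | 1/5: 0.5% to 71.6% |
| 10 | 30.8% | 2/10: 2.5% to 55.6% |
| 15 | 21.8% | 3/15: 4.3% to 48.1% |
| 20 | 16.8% | 4/20: 5.7% to 43.7% |

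At n = 10, only 0/10 excludes the 40% used to design Cohort 1; 1/10 already reaches 44.5%. Even 0/10 does not exclude the 20% threshold. The interval for 2/10 contains both 20% and 40%.

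**The case against.** The strongest defense is that this is an openly declared scaling-down. Section 8 also drops the biomarker and quality-of-life analyses without a specific reason, so most of the exploratory work went together when the study ended. The change is listed where changes belong, safety for both cohorts stays, and the analyses were exploratory in closed cohorts with no stated power. On this view the by-cohort sentence in SAP 6.3 is text carried over from Protocol 10.2, and the specific statement in Section 8 governs.

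Much of this stands. A reader might infer deliberate selective reporting, but nothing in the documents shows that Cohort 2 or 3 outcomes influenced the decision. A reader might also infer that the SAP removes these cohorts because central review was cancelled. Section 8 does not say so, and the supportable point is only that no reason is stated. Nor can it be said that investigator assessment was the plan in every protocol version, since only Version 7.0 is available.

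The value of the missing results can also be overstated. A reader might expect them to show whether activity is confined to Cohort 1. They could not settle that. The estimates would be imprecise. Protocol 3.1 describes Cohort 3 as a mixture: fusions without an EGF-like domain, fusions with other aberrations, and patients without tissue for central confirmation. The Cohort 2 and 3 population has no regimen restriction, and patients enrolled before Protocol Version 4.0 began on induction followed by dosing every two weeks (Appendix A), so regimens may be mixed.

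None of this supplies the missing reason. Dropping other exploratory work, also without a stated reason, does not explain dropping analyses whose assessor and methods were already specified and remain in use for Cohort 1.

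**Conclusion.** The point holds as a reporting gap. Protocol 7.0 plans these analyses, the SAP removes them without a reason, neither the absence of central review nor early stopping accounts for it, and SAP 6.3 and Section 8 disagree as written. The consequence is a risk of selective reporting, with no evidence of intent and no effect on the Cohort 1 analysis or its 89.3% calculated power. The results would be descriptive only; at an assumed 10 patients, most outcomes would leave 40% inside the interval.

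This rests on two assumptions: that patients were treated in Cohorts 2 and 3, inferred from the planned safety tables, and that their investigator tumor assessments were collected, as Protocol 3.1 requires. It is a cheap improvement that should be made.

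**What to change.** 1. Replace the Cohort 2 and 3 sentence in SAP Section 8. Simply deleting it would remove the only disclosure of a departure from Protocol 10.5.3 if any of those analyses stayed out.
2. Restore the Protocol 10.2.2 population definition in SAP 4.1.
3. For each cohort, labelled exploratory and descriptive, report investigator-assessed confirmed ORR with its exact 95% CI and best overall response. Add DoR, PFS, CBR and OS, at least as by-patient listings that show the dosing regimen received and, for Cohort 3, the reason for assignment to that cohort.
4. State in Section 8 any Protocol 10.5.3 analysis that is still reduced to a listing or omitted, with the reason.
5. Align the by-cohort sentence in SAP 6.3 with whatever is decided.

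The cost is a few extra tables or listings per cohort, using methods the SAP already specifies for Cohort 1 and assessments the protocol already requires. The downside is imprecise estimates from possibly mixed regimens, which the labelling and the listings should make plain. Sample size, power and the Cohort 1 analyses do not change.
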